#### 8.9 Events of Clinical Interest

Selected non-serious and serious adverse events are also known as Events of Clinical Interest (ECI) and must be reported to the Sponsor.

For the time period beginning when the consent form is signed until patient registration, any ECI, or follow up to an ECI, that occurs to any patient must be reported within 24 hours to the Sponsor if it causes the patient to be excluded from the trial, or is the result of a protocol-specified intervention, including but not limited to washout or discontinuation of usual therapy, diet, or a procedure.

For the time period beginning at patient registration through 30 days following cessation of treatment, any ECI, or follow up to an ECI, whether or not related to the Sponsor's product, must be reported within 24 hours to the Sponsor, either by electronic media or paper. Electronic reporting procedures can be found in the data entry guidelines.

- 1. An elevated AST or ALT lab value that is  $\ge 3X$  ULN and an elevated total bilirubin lab value that is  $\ge 2X$  ULN and, at the same time, an alkaline phosphatase lab value that is < 2X ULN, as determined by protocol-specified laboratory testing or unscheduled laboratory testing.\*
  - \*Note: These criteria are based upon available regulatory guidance documents. The purpose of the criteria is to specify a threshold of abnormal hepatic tests that may require an additional evaluation for an underlying etiology. The trial site guidance for assessment and follow up of these criteria can be found in Appendix 5 and the Investigator Brochure section on discussion and guidance for investigator.
- 2. An elevated total bilirubin lab value that is  $\geq 2X$  ULN.
- 3. Any of the following liver test abnormalities are observed (see also Appendix 5):
  - ALT or AST > 8X ULN
  - ALT or AST > 5X ULN for more than 2 weeks
  - ALT or AST > 3X ULN AND (total bilirubin > 2X ULN OR INR > 1.5)
  - ALT or AST > 3X ULN with the appearance of fatigue, nausea, vomiting, right upper quadrant pain or tenderness, fever, rash and/or eosinophilia (> 5%)
  - \*\*All patients with these liver test abnormalities should be followed weekly until all abnormalities return to normal or to the baseline state. DILI may develop or progress even after the causative drug has been stopped. Results should be recorded on the case report form and in the database. See Appendix 5 for guidelines on the handling of events of ALT or AST >3 x ULN AND total bilirubin >2 x ULN or INR>1.5 (potential Hy's law cases).

#### 9 EFFICACY ASSESSMENTS

Efficacy will be measured in terms of tumor response, according to either RECIST, or PCWG2 for CRPC patients. Tumor markers will also be assessed; CEA (for NSCLC), CA19-9 and CEA (for PDAC), PSA (for CRPC), CA15-3 (TNBC), and other nonspecific tumor markers as appropriate. Tumor measurements are to be made every 6 weeks and bone scans will be performed every 12 weeks until progressive disease is observed.

#### 9.1 RECIST

Tumor lesions will be assessed throughout the study according to RECIST criteria (version 1.1) (Eisenhauer et al., 2009). Any tumor shrinkage, in terms of percentage of tumor regression, will be reported even if it does not meet RECIST criteria for response. While RECIST criteria (version 1.1) do not require confirmation of objective response in clinical studies where response rate is not the study primary endpoint, as a convincing proof-of-concept of antitumor activity, efforts should be made to confirm objective response at least 4 weeks apart.

# 9.1.1 Imaging Technique

To ensure comparability, the baseline and subsequent tumor measurements to assess response should be performed using identical imaging techniques (i.e., preferably the same machine, contrast agent and standard volume of contrast agent, etc.).

#### 9.1.2 Evaluation of Lesions

Table 12: Evaluation of response in target lesions

Complete Response (CR)	Disappearance of all target lesions. Any pathological lymph nodes (whether target or non-target) must have reduction in short axis to <10 mm.
Partial Response (PR)	At least a 30% decrease in the sum of diameters of target lesions, taking as reference the baseline sum diameters.
Progression (PD)	At least a 20% increase in the sum of diameters of target lesions, taking as reference the smallest sum on study (this includes the baseline sum if that is the smallest on study).  In addition to the relative increase of 20%, the sum must also demonstrate an absolute increase of at least 5 mm.  The appearance of one or more new lesions is also considered progression)
Stable Disease (SD)	Neither sufficient shrinkage to qualify for PR nor sufficient increase to qualify for PD, taking as reference the smallest sum diameters while on study

#### **Table 13: Evaluation of non-target lesions**

Complete Response (CR)	Disappearance of all non-target lesions. All lymph nodes must be non-pathological in size (<10 mm short axis)
Non-CR / Non-PD	Persistence of one or more non-target lesion(s) and/or maintenance of tumor marker level above the normal limits.
Progression (PD)	Unequivocal progression of existing non-target lesions; see Section 4.3.4 of Eisenhauer et al., 2009 for further details.  Note: the appearance of one or more new lesions is also considered progression. Unequivocal progression of existing non-target lesions, other than pleural effusions without cytological proof of neoplastic origin, in the opinion of the treating investigator (in this circumstance an explanation
	must be provided)  .

Although clear progression of non-target lesions only is exceptional, in such circumstances, the opinion of the treating physician should prevail and the progression status should be confirmed later by the Medical Monitor.

# 9.1.3 Definition of Best Overall Tumor Response

The best overall response is the best response recorded between the start and the end of treatment, as described below. Overall response is calculated for each assessment time point according to Table 14.

Table 14: Overall response in patients with target (+/- non-target) disease

Target lesions	Non-target lesions	New lesions	Overall response
CR	CR	No	CR
CR	Non-CR/non-PD	No	PR
CR	Not evaluated	No	PR
PR	Non-PD or not all evaluated	No	PR
SD	Non-PD or not all evaluated	No	SD
Not all evaluated	Non-PD	No	NE
PD Any		Yes or No	PD
Any PD		Yes or No	PD
Any Any Yes Pl		PD	

CR, complete response; PR, partial response; SD, stable disease; PD, progressive disease; NE, not evaluable

The best overall response is determined once all data for a given patient are available. Table 15 below summarizes the best overall tumor response.

Table 15: Best overall response

Overall response	Overall response	Best overall response
First time point	Subsequent time points	
CR	CR	CR
CR	PR	SD, PD or PR 
CR	SD	SD provided minimum criteria for SD duration met, otherwise, PD
CR	PD	SD provided minimum criteria for SD duration met, otherwise, PD
CR	NE	SD provided minimum criteria for SD duration met, otherwise NE
PR	CR	PR
PR	PR	PR
PR	SD	SD
PR	PD	SD provided minimum criteria for SD duration met, otherwise, PD
PR	NE	SD provided minimum criteria for SD duration met, otherwise NE
NE	NE	NE

CR, complete response; PR, partial response; SD, stable disease; PD, progressive disease; NE, not evaluable

1. If a CR is truly met at first time point, then any disease seen at a subsequent time point, even disease meeting PR criteria relative to baseline, makes the disease PD at that point (since disease must have reappeared after CR). Best response would depend on whether minimum duration for SD was met. However, sometimes CR may be claimed when subsequent scans suggest small lesions were likely still present and in fact the patient had PR, not CR at the first time point. Under these circumstances, the original CR should be changed to PR and the best response is PR.

Patients with a global deterioration of health status requiring discontinuation of treatment without objective evidence of disease progression at that time should be reported as "symptomatic deterioration". Every effort should be made to document the objective progression even after discontinuation of treatment.

For equivocal findings of progression (e.g. very small and uncertain new lesions; cystic changes or necrosis in existing lesions), treatment may continue until the next scheduled assessment. If at the next scheduled assessment, progression is confirmed, the date of progression should be the earlier date when progression was suspected.

In some circumstances it may be difficult to distinguish residual disease from normal tissue. When the evaluation of complete response depends upon this determination, it is recommended that the residual lesion be investigated (fine needle aspirate/ biopsy) before confirming the complete response status.

#### 9.2 **PCWG2**

For CRPC patients, PSA response rates will be measured according to the PCWG2 criteria (Scher et al., 2008). RECIST v1.1 is used to assess soft tissue disease (Eisenhauer et al., 2009). Progression of bone disease is defined using PCWG2 criteria, namely a confirmed increase of at least two new lesions on a bone scan.

#### 9.2.1 PSA

# For control/relief/eliminate end points

The PCWG2 advises against reporting PSA response rates because they are of little value given the uncertain significance of a defined degree of decline from baseline, be it 50% or 30%, and no criterion has been shown prospectively to be a surrogate of clinical benefit (Fleming et al., 2006).

To report PSA-based outcomes, PCWG2 recommends that the percentage of change in PSA from baseline to 12 weeks (or earlier for those who discontinue therapy), as well as the maximum decline in PSA that occurs at any point after treatment be reported for each patient using a waterfall plot (Seidman et al., 1992). Waterfall plots provide a broader and more sensitive display of data, and are more informative until a validated surrogate of clinical benefit becomes available. PCWG2 recommends that the same waterfall plot be used to illustrate outcomes for noncytotoxic agents. It discourages the use of changes in PSA-doubling time or PSA slope as a primary end point, given that their clinical significance is uncertain, and also recommends avoiding reporting duration of PSA control, as described in PCWG1 guidelines, because its interpretation varies between investigators.

#### For delay/prevent end points

PCWG2 defines PSA progression as the date that a 25% or greater increase and an absolute increase of ≥2 ng/mL from the nadir is documented, which is confirmed by a second value obtained 3 or more weeks later. This will be used to determine both PSA progression and response duration. This recommendation recognizes that variations in progression times might occur simply on the basis of the rate of PSA rise. Where no decline from baseline is documented, PCWG2 defines PSA progression as a 25% increase from the baseline value along with an increase in absolute value of 2 ng/mL or more (rather than 5 ng/mL) after 12 weeks of treatment.

# 9.2.2 Measurable Soft-Tissue Lesions

# For control/relieve/eliminate end points

PCWG2 accepts with modifications RECIST criteria for evaluating drugs or approaches anticipated to produce tumor regression. The modifications are that changes in nodal and visceral sites be recorded and reported separately, and lymph nodes in the pelvis must measure at least 2 cm in their greatest diameter to

be considered target lesions. PCWG2 also recommends that the complete elimination of disease at a particular site be recorded separately. PCWG2 reinforces the recommendation in RECIST that any favorable change should be confirmed using a second follow-up scan. As with changes in PSA, PCWG2 suggests that changes in the size of the target lesions be reported as a waterfall plot to facilitate comparison between studies.

### For prevent/delay end points

Progression in a nodal or visceral site should also be defined using RECIST, with the recognition that, for some therapies, early unfavorable changes may not accurately reflect disease status. As noted, a lymphocytic infiltration of a tumor mass after successful immunization may result in an enlarged soft-tissue lesion that could be an early indication that the treatment is working. Further, because the effects of some agents (non-cytotoxic) may be delayed, the degree of increase in tumor size at the first 12-week assessment should also be confirmed before it is considered a treatment failure.

#### 9.2.3 Bone

Given the frequency of bone involvement in patients with progressive, castration-resistant disease, the decreased emphasis of early changes in PSA, and the increased availability of cytostatic agents, reliable methods to assess changes in bone are of increasing importance. PCWG2 recognizes that standards for using MRI and PET to assess bone metastases are under active investigation, so only radionuclide bone scans are considered here. PCWG2 also recognizes that there are no validated criteria for response on radionuclide bone scan.

#### For control/relieve/eliminate end points

PCWG2 recommends that post-treatment changes be recorded simply as either "no new lesions" or "new lesions." However, progression at the first scheduled assessment should be confirmed on a second scan performed 6 or more weeks later, in the absence of clearly worsening soft-tissue (nodal and visceral) disease or disease-related symptoms. In the rare case where visible lesions disappear, this too should be confirmed at the next scheduled assessment.

#### For prevent/delay end points

Progressing disease on bone scan is considered when a minimum of two new lesions is observed. PCWG1 made the provision that a worsening bone scan on the first follow-up manifests tumor "flare"; PCWG2 does not recommend performing a follow-up bone scan before 12 weeks of treatment unless clinically indicated. At the first 12-week reassessment, defining disease progression requires a confirmatory scan (which shows additional new lesions compared with the first follow-up scan) performed 6 or more weeks later, because lesions visible at the 12-week assessment may represent disease that was not detected on the pretreatment scan. When further progression is documented on the confirmatory scan, the date of progression recorded for the trial, is the date of the first scan that shows the change.

Note that symptoms will not be evaluated in this phase Ib study.

Table 16: The Prostate Cancer Clinical Trials Working Group (PCWG2) Response Criteria

Variable	PCWG2 Criteria (Scher et al., 2008)
PSA	For control/relieve/eliminate end points:
	Record the percent change from baseline (rise or fall) at 12 weeks, and separately, the
	maximal change (rise or fall) at any time using a waterfall plot
	Progression:
	Decline from baseline : record time from start of therapy to first PSA increase that is $\geq$
	25% and $\geq$ 2 ng/mL above the nadir, and which is confirmed by a second value 3 or
	more weeks later (i.e., a confirmed rising trend)
	The requirement of an increase of 5 ng/mL is decreased to 2 ng/mL, and the
	requirement for a 50% increase is reduced to 25%
	Recording the duration of PSA decline of little value
	No decline from baseline:
	PSA progression $\geq 25\%$ and $\geq 2$ ng/mL after 12 weeks
Soft-tissue	For control/relieve/eliminate end points:
lesions	
	Use RECIST with caveats
	Only report changes in lymph nodes that were $\geq 2$ cm in diameter at baseline
	Record changes in nodal and visceral soft tissue sites separately
	Record complete elimination of disease at any site separately
	Confirm favorable change with second scan
	Record changes using waterfall plot
	For delay/prevent end points:
	Use RECIST criteria for progression, with additional requirement that progression at
	first assessment be confirmed by a second scan 6 or more weeks later
D	Note that for some treatments, a lesion may increase in size before it decreases
Bone	For control/relieve eliminate end points:
	Record outcome as new lesions or no new lesions
	First scheduled reassessment:
	No new lesions: continue therapy
	New lesions: perform a confirmatory scan 6 or more weeks later
	Confirmatory scan: No new lesions: continue therapy
	Additional new lesions: progression Subsequent scheduled reassessments:
	No new lesions: continue
	New lesions: progression
	For prevent/delay end points (progression):
	The appearance of $\geq 2$ new lesions, and, for the first reassessment only, a confirmatory
	scan performed 6 or more weeks later that shows a minimum of 2 or more additional
	new lesions
	The date of progression is the date of the first scan that shows the change
	The date of progression is the date of the first sean that shows the change

PSA, prostate-specific antigen

#### 10 PHARMACOKINETICS ASSESSMENTS

#### 10.1 Sample collection

PK sampling will be performed in all patients enrolled in the dose escalation phase and selected patients from the expansion cohort.

A plasma sampling schedule including a total of 6 time-points over the first 7 hours of **day 1 of cycle 1** will be performed to characterize the PK profile of OTX015 ( $C_{max}$ ,  $C_{min}$ ,  $T_{max}$ , AUC  $_{[0-\infty]}$ , Vd $_{ss}$ ,  $t_{1/2}$ , and CL), as follows: **T0** (immediately before OTX015/MK-8628 intake), **T15min** ( $\pm 5$  min), **T1h** ( $\pm 15$ min), **T2h** ( $\pm 15$ min), **T7h** ( $\pm 15$ min) post-dose.

Blood samples of 3.0 mL will be collected in EDTA tubes, inverted a few times to mix the anticoagulant and then processed as soon as possible (within 15 min). Samples will be centrifuged at 1500 g (4,000 rpm for a 14-15 cm centrifuge) at +4°C for 10 minutes. Plasma will be immediately aliquoted and stored in airtight stoppered polypropylene tubes at -20°C.

In total, six blood samples of 3.0 mL each will be collected, i.e. approximately 18 mL of blood will be drawn per patient from a peripheral venous access for PK analysis.

Blood samples must be sent as soon as possible to the laboratory for analysis, to allow for availability of results at the SMC meeting. If two patients in the same center are treated at the same time or a few days apart, samples of these two patients should be sent together.

All samples will be labeled with:

- Sponsor and Protocol Number
- UPN and patient initials
- Sample number with actual date and time of collection

All samples must be shipped at -20°C to:

### 10.2 Assay Method and Parameters Analyzed

Plasma concentrations of OTX015/MK-8628 will be measured using Ultra Performance Liquid Chromatography with tandem Mass Spectrometry detection (UPLC-MS/MS).

The following parameters will be determined: Trough ( $C_{min}$ ) and peak ( $C_{max}$ ) concentrations,  $T_{max}$ ,  $AUC_{[0-1]}$ ,  $Vd_{ss}$ ,  $t_{1/2}$ , steady state, total clearance (CL).

Descriptive statistics will be used to summarize PK parameters with mean, standard deviation (SD), coefficient of variation (CV) and ranges. Analyses will be carried out using the nonlinear mixed effect modeling software program Monolix version 3.2s (http://wfn.software.monolix.org).

PK data for OTX015/MK-8628 will be interpreted in terms of safety findings and compared with historical data.

#### 11 STATISTICAL CONSIDERATIONS

#### 11.1 Statistical Design and Sample Size

The exploratory part of the study is designed to assess the safety of OTX015/MK-8628 in patients with advanced or metastatic solid tumors. The small numbers per cohort are not intended for statistical hypotheses. Treatment decisions will be made by the SMC. The expansion cohort part will start once the MTD and a regimen are determined.

In the dose escalation part, up to 48 patients evaluable for DLT (i.e. up to 24 patients per regimen) will be accrued depending on the number of DLTs encountered. Once the MTD is established with at least 3 patients having received at least 2 cycles of study drug, an expansion cohort of up to 50 additional evaluable patients (10 patients per indication) will be enrolled. The regimens used in the expansion cohort will be decided for each indication by the SMC.

The final sample size will depend on the number of DLTs encountered at each DL and in each regimen, and may be increased if within the two proposed regimens and four planned DLs, the MTD is not reached and additional DLs are required.

# 11.2 Study Endpoints

Primary: The number of patients experiencing at least one DLT in cycle 1 (day 1 to 21) for each of the two regimens independently.

#### Secondary:

*Safety*: Incidence, severity and relationship of AEs, laboratory abnormalities, SAEs, discontinuations due to AEs, dose adaptations due to AEs, and DLT.

*Efficacy*: The number of patients with clinical benefit (defined as complete response, partial response or stable disease) and progressive disease based on the best overall response from tumor evaluations performed every 2 cycles, according to RECIST v1.1 or PCWG2, and tumor marker assessment.

*Pharmacokinetics*: Plasma parameters of OTX015/MK-8628 including  $C_{max}$ ,  $C_{min}$ ,  $T_{max}$ , AUC  $_{[0-\infty]}$ ,  $Vd_{ss}$ ,  $t_{1/2}$ , CL.

#### 11.3 Analysis Populations

- Evaluable for DLT: patients who receive at least 85% of the planned dose of study drug (18 days for Regimen 1, or 6 days for Regimen 2) or experience DLT during the first 21-day cycle.
- Treated population: patients who receive at least one dose of study drug.
- Evaluable for efficacy: patients who receive at least 2 complete cycles (6 weeks) of treatment and have undergone baseline assessment and one on-study tumor assessment, or who discontinue early due to disease progression.

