#### **EVALUATION CRITERIA**

## **Evaluation Populations**

Evaluable for DLT: patients who receive at least 85% of the planned dose of study drug (18 days for Regimen 1, or 6 days for Regimen 2) or experience DLT during the first 21-day cycle.

Treated population: patients who receive at least one dose of study drug.

Evaluable for efficacy: patients who receive at least 2 complete cycles (6 weeks) of treatment and have undergone baseline assessment and one on-study tumor assessment, or who discontinue early due to disease progression.

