#### Statistical Methods

The dose escalation part of the study is designed to assess the safety of OTX015/MK-8628 in this patient population. The small numbers per cohort are not intended for statistical hypotheses. Treatment decisions will be made by the SMC.

The expansion cohort part will start once the MTD and a regimen are determined. Ten patients will be enrolled per indication to give a total of 50 evaluable patients for efficacy.

Quantitative variables will be summarized using descriptive statistics. Continuous variables will be presented as N, mean and/or median, standard deviation, range. Categorical variables will be presented using frequencies and percentage.

Patient disposition and demographics will be analyzed in all included patients, response will be analyzed in patients evaluable for efficacy, and safety will be analyzed in the treated population with an additional analysis in patients evaluable for DLT for the dose escalation part.

Data will be analyzed according to dose level and regimen for the dose escalation part of the study, and according to indication and/or regimen for the dose expansion part of the study.

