#### Safety Findings

## Extent of Exposure

The number of treatment cycles, dose reductions, dose interruptions, and reasons for treatment discontinuation for the 63 treated patients is summarized in Table 3 and Table 4 below.

The majority of patients (63%) discontinued OTX015 treatment due to disease progression, and among the 52 patients who could have received at least 3 cycles (i.e., more than 9 weeks elapsed between study treatment initiation and the cut-off date of the present report), 17 (33%) had received more than 3 cycles (median 5.0; range 4-14+).

Study treatment was interrupted for more than one day in 15 patients due to related AEs, 9 with grade 3-4 thrombocytopenia, two with grade 4 neutropenia, and one each with aminotransferase elevation, coagulation factor VII decrease and fever of unknown origin, aggravation of diabetes mellitus, and grade 3 hyponatremia.

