**Country** 

Table 4: Patient exposure in treated acute leukemia patients (N=30)

Dose	10 mg QD 14/21 N=3	20 mg QD 14/21 N=3	40 mg QD 14/21 N=4	80 mg QD 14/21 N=3	40 mg BID 14/21 N=8	120 mg QD 14/21 N= 3	120 mg QD 21/21 N=3	160 mg QD 14/21 N=3*	Total N=30*
Median (range) # cycles	6 (1-7)	3 (2-4)	3 (1-14+)	5 (1-5)	2 (<1-8)	2 (2-3)	2+ (2-3+)	2+ (1+-3+)	2 (<1-14+)
Dose reduction	0	0	0	0	0	0	0	2	2
Intrapatient dose escalation	1 (20 mg)	0	1 (120 mg)	0	0	0	0	0	2
Dose interruption > 1 day	2	1	2	0	1	0	0	0	(
_	(unrelated)	(unrelated)	(1 unrelated)	0	1	U	U	U	6
Reason for study treatment d	iscontinuatio	n							
Tumor progression	2	3	1	3	5	3	0	0	17
Consent withdrawal	1	0	1		1	0	0	0	3
Deterioration general condition	0	0	1	0	0	0	0	0	1
No further benefit	0	0	0	0	1	0	0	0	1
Early death (unrel)	0	0	0	0	1	0	1	0	2
Treatment ongoing	0	0	1	0	0	0	2	3	6

\*One additional patient (AL cohort, DL6, 160 mg QD 14 / 21) was enrolled but not yet treated due to leukemia-related sepsis

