#### 3.3 Study Duration and Dates

Patients will begin treatment within a week after registration, followed by the treatment period (3-week cycles), and a follow-up period of at least 2 treatment cycles after the last patient has started treatment.

**Study period:** patients are on the study from the time of Informed Consent Form (ICF) signature until the last visit or death, whichever comes first.

**Treatment period:** the time from the initiation of study therapy until the last study drug intake, plus a 30 day safety observation period during which OTX015/MK-8628-related TEAEs are reported.

**End of study:** the study is considered completed after the last patient has been evaluated for efficacy with a follow-up of at least 2 cycles.

The duration of this study will depend on the number of DLTs encountered in each regimen, the number of dose levels explored in each regimen and the rate of accrual in each of the five expansion cohorts.

The study will be closed after the last visit of the last patient still on study.

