#### **5.3** Treatment Duration

Patients will continue study treatment until any of the following events at which point it will be definitively discontinued:

- Disease progression
- Unacceptable toxicity
- Patient withdrawal of consent
- Patient non-compliance
- Treatment interruption for > 2 weeks for any reason (except in the event of perceived benefit, with Sponsor agreement)
- Recurrence of DLT despite dose reduction (except in the event of perceived benefit, with Sponsor agreement)
- Any of the following liver test abnormalities\*\* (see Appendix 5)
  - ALT or AST > 8 x ULN
  - ALT or AST > 5 x ULN for > 2 weeks
  - ALT or AST > 3 x ULN and (total bilirubin > 2 x ULN OR INR > 1.5)
  - ALT or AST > 3 x ULN with the appearance of fatigue, nausea, vomiting, right upper quadrant pain or tenderness, fever, rash and/or eosinophilia (> 5%)

However, in case of investigator's perceived benefit for the patient, treatment continuation can be considered with dose reduction despite delay/interruption > 2 weeks or reoccurrence of a DLT with the same intensity after one dose reduction. The perceived benefit of the investigator is defined by 1) any objective tumor response, or 2) any tumor shrinkage not meeting standard response criteria, but which could improve with additional treatment, or 3) any symptomatic improvement, which, in the investigator's opinion, could not be achieved by other means. If, in the cases described above, DLT recurs with the same intensity despite one dose reduction, a second dose reduction may be considered. The decision should be discussed with the Sponsor, but the final decision must be made by the investigator.

[figure not shown]
In all cases, the reason for and date of study treatment discontinuation must be recorded in the eCRF and source documented in the patient's medical records. As far as possible, there should be only one reason for treatment discontinuation. If there are several (e.g. concomitant progressive disease and toxicity), the primary one must be reported. The patient must be followed up to establish whether the reason was a TEAE, and if so, this must be reported as such.

As far as possible, all examinations scheduled for the final study day must be performed for all patients who receive the investigational product but who do not complete the study according to protocol.

The investigator must make every effort to contact patients lost to follow-up, especially when a patient is treated in another non-study center.

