# A visit will be performed 35 days (±5 days) after the last OTX015/MK-8628 intake, including the following:

Physical examination, PS, vital signs, body weight

- CBC
- INR, Factor VII
- Serum chemistries
- Concomitant medications
- Adverse events
- Tumor imaging
- Tumor markers

The last patient will be followed-up for at least two cycles after treatment initiation to allow for evaluation of efficacy.

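### Response is analysed only in an efficacy-evaluable set that keeps early leavers only if they progressed, and no all-treated analysis is planned beside it

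*Protocol*

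**What the plan says.** Protocol 11.3 and SAP 2.5 define the efficacy set in the same way. A patient enters by one of two routes. The first covers "patients who receive at least 2 complete cycles (6 weeks) of treatment and have undergone baseline assessment and one on-study tumor assessment". The second route is for early leavers and admits only one reason for leaving; the synopsis words it as "or who discontinue early due to disease progression". Protocol 11.4, the synopsis and SAP 2.6 assign response to this set and to no other. The treated population (at least one dose) is defined in both documents but used for safety. All included patients are used for disposition and demographics. No missing data are imputed, and no rule places non-evaluable patients in the response denominator.

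The efficacy endpoint (Protocol 11.2, SAP 2.4) is the number of patients with clinical benefit (CR, PR or SD) and with progression, from best overall response. Categorical results are shown as frequencies and percentages, by dose level and regimen.

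Protocol 5.3 lists the reasons for stopping: "Patients will continue study treatment until any of the following events at which point it will be definitively discontinued". Besides progression these include unacceptable toxicity, withdrawal of consent, non-compliance, four liver-test criteria, and an interruption of more than 2 weeks, the last with an exception for perceived benefit. Protocol 7.3 adds a final assessment: "A visit will be performed 35 days (±5 days) after the last OTX015/MK-8628 intake". Its list of procedures includes tumor imaging.

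**The concern.** For patients who leave before 6 weeks, the reason for leaving decides whether they count. Progressors stay, and everyone else goes. The set is thus selected partly on outcome, and a benefit percentage taken from it need not describe the patients who were treated.

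The exclusion can also be tied to tolerability. The liver-test criteria that define a DLT in Protocol 5.2.4 are the same ones that end treatment in 5.3. A patient who meets one in cycle 1 and stops without progression counts in the DLT analysis but drops out of the response analysis. This follows from the rules; the documents do not show how often it happens.

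Protocol 1.4.2 says that running two regimens in parallel will allow one to be chosen on the balance of tolerability, pharmacokinetics and antitumor activity. If different dose levels or regimens lose different kinds of patients, their activity percentages are not strictly comparable.

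**Working it through.** **1. The plan's own counts.** Protocol: 2 regimens × 4 dose levels × 6 = 48; 5 indications × 10 = 50; 48 + 50 = 98, as stated in Protocol 4.1. SAP 2.2: 3 dose levels × 14 = 42; 48 + 42 = 90, as stated. All reproduce. None says how many treated patients will fall outside the efficacy set.

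**2. Who is in and who is out.**
- At least 2 complete cycles, baseline and one on-study assessment: in.
- Stop before 6 weeks for progression: in.
- Stop before 6 weeks for toxicity, liver tests, interruption over 2 weeks without the perceived-benefit exception, withdrawal, non-compliance, or death without progression: out.

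The last group can still have imaging. A patient whose last dose is on day 21 is due a visit on days 21 + 30 = 51 to 21 + 40 = 61. That scan cannot bring the patient into the set, because the 2-cycle condition is not met.

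**3. Size as a function of assumptions.** Let x be the share of treated patients excluded, r the benefit rate in those kept and b the rate in those excluded. The documents give none of these for this trial. Then

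evaluable rate / all-treated rate = r / [r(1 − x) + bx].

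If b = 0 this is 1/(1 − x):
- x = 10%: 1/0.90 = 1.11
- x = 20%: 1/0.80 = 1.25
- x = 30%: 1/0.70 = 1.43

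If excluded patients did better, the ratio falls below 1. With r = 30% and b = 50%, assumed only to show the reverse case:
- x = 10%: 0.30/0.32 = 0.94
- x = 20%: 0.30/0.34 = 0.88
- x = 30%: 0.30/0.36 = 0.83

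**4. Against sampling error.** The protocol synopsis plans cohorts of ten: "Ten patients will be enrolled per indication to give a total of 50 evaluable patients for efficacy". SAP 2.2 no longer lists these cohorts, so this is an illustration of scale. Suppose 3 of 10 evaluable patients benefit: 30.0%, exact 95% CI 6.7% to 65.2%. Suppose two more were treated but excluded. The all-treated result is then:
- 3/12 = 25.0% (5.5% to 57.2%) if neither had benefit
- 4/12 = 33.3% (9.9% to 65.1%) if one did
- 5/12 = 41.7% (15.2% to 72.3%) if both did

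The shift is well inside the interval.

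**5. Context from the hematology study.** Protocol 1.3.3.2 reports: "The majority of patients (63%) discontinued OTX015 treatment due to disease progression". The row totals of its Tables 4 and 5 give 17 + 23 = 40 stops for progression, and 40/63 = 63%, which agrees. Other stops are 7 in acute leukemia (3 withdrawals, 1 deterioration, 1 no further benefit, 2 early deaths) and 2 in the other malignancies (1 unrelated adverse event, 1 transplant). That is 9/63 = 14.3% (exact 95% CI 6.7% to 25.4%). Ongoing: 6 + 8 = 14. Check: 40 + 9 + 14 = 63.

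**The case against.** The case for leaving the plan alone is substantial. The endpoint is secondary and descriptive, no hypothesis is tested, and no response threshold drives a decision. An evaluable set is usual in phase I. The endpoint is worded as a number of patients; if nobody excluded had benefit, that number does not change. Disposition and reasons for stopping are recorded for everyone, so a reader can divide the reported count by the treated number and recover the b = 0 case unaided. The most obvious route to inflation is closed, because early progressors are kept. In the hematology study they were 40 of 49 stops (82%). The perceived-benefit exception in Protocol 5.3 also tends to keep benefiting patients on drug, which makes the reverse case less likely.

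Most of this stands, and it limits the weight of the point. It does not remove it. The percentages that are reported would still use the selected set, and an early leaver with a usable scan would remain uncounted; no division by treated numbers can restore that patient. Disposition tables show why patients stopped but do not link this to response.

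**Conclusion.** The point holds as a reporting gap in a secondary, descriptive analysis. The evaluable set is selected partly on outcome and stands alone. The ratios of 1.11, 1.25 and 1.43 rest on two assumptions: the loss rate, and no benefit among those excluded. Sample size, DLT counts and MTD are unaffected.

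A reader might infer more than the documents support:
- *That activity will be overstated.* Keeping early progressors limits upward bias, and an excluded patient may have stable disease on the final scan. The direction is not certain.
- *That 14% is the expected loss here.* The 9/63 covers all follow-up in other diseases, not stops before 6 weeks. Nor do those tables show that losses rise with dose: none of the nine is listed as related toxicity.
- *That the patient transplanted in PR shows responders being excluded.* Nothing shows that this patient would have failed the 2-cycle rule.
- *That the final scan falls outside a response window.* The 30 days after last intake in Protocol 3.3 are a safety observation period and do not govern response.
- *That excluded patients cannot be classified.* Table 15 in Protocol 9.1.3 is not limited to the evaluable set; only the summary population is.

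The minimum duration of stable disease, which Table 15 mentions without a value, and the handling of symptomatic deterioration are separate side notes and are not needed for this conclusion.

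**What to change.** In SAP 2.6, keep the evaluable-set analysis and add beside it:
- best overall response and clinical benefit in all treated patients, using any available post-baseline scan, including the end-of-treatment scan;
- patients without a post-baseline assessment shown as not evaluable and kept in the denominator;
- the number excluded from the evaluable set, with reasons, by dose level and regimen.

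Date the addition and label it as made after some outcomes were known: SAP 2.6 already drops the waterfall plots for prostate cancer because no response had been seen there.

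The cost is one extra table from data already collected, and percentages that may look less favourable. No further patients or visits are needed.
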